#### *11.4.2.1.1 Analysis of annualized event rate*

The annualized rate of exacerbation events, including severe exacerbation events resulting in hospitalization or emergency room visit and LOAC events, will be analyzed using the same way as for severe exacerbation events.

#### *11.4.2.1.2 Analysis of Time to event variables*

Time to event (eg, LOAC, severe exacerbation) will be analyzed using a Cox regression model with time to event as the dependent variable, and treatment, age, number of asthma exacerbation events within 1 year prior to the study, region (pooled country), baseline eosinophil strata and baseline ICS dose level as covariates. The Kaplan-Meier method will be used to respectively estimate the probabilities that a patient would experience events at Week 12, 24, 36 and 52 per each treatment group.

#### *11.4.2.1.3 Analysis of change from baseline for other continuous variables*

The change from baseline for other continuous endpoints will be analyzed using MMRM in the same fashion as for the endpoint of FEV1. The covariates to be included are treatment, age, region (pooled country), baseline eosinophil strata, baseline ICS dose level, visit, treatment-by-visit interaction, corresponding baseline value and baseline-by-visit interaction. Sex and height will be included as covariates only in the models for spirometry parameters.

Descriptive statistics including number of patients, mean, standard error and LS means will be provided. In addition, differences in LS means, the corresponding 95% CI and the p-value will be derived from the MMRM model for comparison of dupilumab against placebo.

Change from baseline at other time points will be analyzed in the same way.

#### *11.4.2.1.4 Subgroup analysis*

To assess the consistency in treatment effects across the subgroup levels, subgroup analyses will be performed for the primary efficacy endpoints with respect to baseline eosinophil level ( $\geq 300$  cells / $\mu$ L vs.  $< 300$  cells / $\mu$ L and  $\geq 150$  cells / $\mu$ L vs.  $< 150$  cells / $\mu$ L), age group, gender, region, race, background ICS dose levels, background controller medication type, baseline FEV1, predicted FEV1 %, ACQ-5, weight, BMI, smoking history, atopic medical history, age of onset of asthma and number of asthma exacerbation events within 1 year prior to the study.

#### **11.4.2.2 Multiplicity considerations**

To strongly control the type-I error rate for the primary family (two primary endpoints and two doses), a hierarchical testing procedure will be applied at a 2-sided 5% significant level, ie, each hypothesis will be formally tested only if the preceding one is significant at the 5% level. The

hierarchy of the tests will be: 1) annualized severe exacerbation rate for 300 mg q2w versus placebo, 2) absolute change from baseline in FEV1 at Week 12 for 300 mg q2w versus placebo, 3) annualized severe exacerbation rate for 200 mg q2w versus placebo, 4) absolute change from baseline in FEV1 at Week 12 for 200 mg q2w versus placebo.

If both doses are significant for both primary endpoints, a selective set of secondary endpoints will be tested following a hierarchical testing procedure at a 2-sided 5% significant level. The list of secondary endpoints to be tested in the hierarchical order will be specified in SAP. The overall familywise error rate will be strongly controlled at a 2-sided 5% level for all tested endpoints across dose groups.

#### 11.4.2.3 Handling of missing data

Sensitivity analyses excluding the additional off-treatment measurements up to Week 52 will be performed to corroborate the primary analyses. The reason and pattern of missing data will be carefully examined and tipping point analysis and additional sensitivity analyses may be performed. The details will be specified in the SAP.

#### **11.4.2.4 Loading dose evaluation**

To examine if inclusion of the loading dose may impact demonstration sustained efficacy regard to exacerbations, additional sensitivity analyses of the annualized rate of severe exacerbation will be performed by excluding severe exacerbation events occurring during the first four weeks and 12 weeks, respectively. The analyses will be performed the same way as the primary analysis. To avoid possible confounding effect due to off-treatment data, only on-treatment events will be included. Due to potential insufficient number of events after excluding data from the first 12 weeks, two dupilumab groups will be combined and two placebo groups will be combined.

#### **11.4.3 Analyses of safety data**

The summary of safety results will be presented by treatment group. The results of the two placebo groups will be presented separately. All safety analyses will be performed on the safety population using the following common rules:

The baseline value is defined generally as the last available value before the first dose of IMP.

The following definitions will be applied to laboratory parameters, vital signs and ECG.

- The potentially clinically significant abnormality (PCSA) values are defined as abnormal values considered medically important by the Sponsor according to predefined criteria/thresholds based on literature review and defined by the Sponsor for clinical laboratory tests, vital signs and ECG.
- PCSA criteria will determine which patients had at least 1 PCSA during the on-treatment period, taking into account all evaluations performed during the on-treatment period, including unscheduled or repeated evaluations. The number of all such patients will be the numerator for the on-treatment PCSA percentage.

### **11.4.3.1 Adverse events**

Adverse event incidence tables will present by system organ class (SOC) (sorted by internationally agreed order), high-level group term (HLGT), high level term (HLT) and preferred term (PT) sorted in alphabetical order for each treatment group, the number (n) and percentage (%) of patients experiencing an AE. Multiple occurrences of the same event in the same patient will be counted only once in the tables within a treatment phase. The denominator for computation of percentages is the safety population within each treatment group.

Proportion of patients with at least one treatment emergent adverse event (TEAE), serious TEAE and TEAE leading to discontinuation of the study will be tabulated by treatment group. In addition TEAEs will be described according to maximum intensity and relation to the study drug. None treatment emergent serious AE, None treatment emergent AE leading to study discontinuation will be summarized separately.

#### **11.4.3.1.1 AESI**

The following summaries will be generated:

- Incidence of each AESI will be tabulated by treatment group.
- The time-to-first event analyzed using K-M methods and displayed as K-M plots (cumulative incidence (%) versus time based on K-M estimates) will be provided to depict the course of onset over time. When TEAE start date or worsening date is partially available, the maximum of the earliest possible TEAE start date and the treatment start date will be used. When TEAE start date or worsening date is completely missing, the treatment start date will be used.
- An overview summary of the number (%) of patients with
  - any TEAE
  - any serious AE (regardless of treatment-emergent status)
  - any treatment-emergent SAE
  - any AE leading to death
  - any TEAE leading to permanent study drug discontinuation
  - any TEAE by maximum intensity, corrective treatment, and final outcome
  - cumulative incidence at specified time points (K-M estimates at 1 week, 4 weeks, 12 weeks, 24 weeks and 52 weeks)

AESI definitions and the method to identify AESIs will be specified in the SAP.

#### **11.4.3.1.2 Death**

The following deaths summaries will be generated:

- Number (%) of patients who died by study period (TEAE, on-study) and reasons for death summarized on the safety population by treatment received

- Death in nonrandomized patients or randomized and not treated patients
- TEAE leading to death (death as an outcome on the AE CRF page as reported by the Investigator) by primary SOC , HLGT, HLT and PT showing number (%) of patients sorted by internationally agreed order of SOC and alphabetic order of HLGT, HLT, and PT.

Patient data listings will be provided for all AEs, TEAEs, SAE, AEs leading to study discontinuation, AESIs and deaths.

#### ***11.4.3.1.3 Clinical Laboratory Evaluation, Vital Signs and electrocardiogram data***

Results and change from baseline for the parameters will be summarized by treatment group for baseline and each post baseline time point, endpoint, minimum and maximum value. Summary statistics will include number of patients, mean, standard deviation, median, Q1, Q3, minimum and maximum.

The proportion of patients who had at least one incidence of PCSA at any time during the TEAE period will be summarized by treatment group. Shift tables showing changes with respect to the baseline status will be provided.

Listings will be provided with flags indicating clinically out-of range values, as well as PCSA values.

#### ***11.4.3.2 Vaccine response***

For patients who receive vaccination, vaccine response parameters will be summarized by treatment groups with descriptive statistics.

#### **11.4.4 Analyses of systemic drug concentration, anti-drug antibodies and pharmacodynamic variables**

##### ***11.4.4.1 Drug concentration analysis***

Concentrations of functional dupilumab in serum will be summarized using arithmetic and geometric means, SD, standard error of the mean (SEM), coefficient of variation (CV%), minimum, median, and maximum by treatment per visit.

Concentrations of functional dupilumab in serum will be used for population PK analysis by non-linear mixed effects modeling if warranted. Additional details of the analysis plan and the results will be provided in a separate document.

##### ***11.4.4.2 Anti-drug antibodies analysis***

Incidence of positivity in the ADA assay will be assessed as absolute occurrence (n) and percent of patients (%), presented by study cohorts. Listing of all ADA titer levels will be provided for

patients positive in the ADA assay. All samples that are positive in the ADA assay will be further tested for the presence of anti-dupilumab neutralizing antibodies.

Plots of concentrations of functional dupilumab will be examined and the potential influence of ADA on individual concentration-time profiles will be evaluated. Assessment of the potential impact of ADA on safety and efficacy may be provided.

ADA at baseline will be summarized by:

- Number (%) of patients with a baseline sample negative in the ADA assay.
- Number (%) of patients with a baseline sample positive in the ADA assay.
- The summary statistics (including number, median, Q1, Q3, minimum and maximum) of the titer for patients positive in the ADA assay at baseline.

ADA incidence and titer will be provided for the following:

- Number (%) of patients negative in ADA assay at all times
- Number (%) of patients positive in ADA assay at any time
- Number (%) of patients with treatment-emergent ADA
- The summary statistics (including number, median, Q1, Q3, minimum and maximum) of the peak post-baseline titer for patients with treatment-emergent ADA
- Number (%) of patients with transient treatment-emergent ADA
- Number (%) of patients with persistent treatment-emergent ADA

Titer values (Titer value category)

The minimum titer for samples positive in the ADA assay is based on the minimum required dilution of the assay.

Low (Titer < 1000)  
Moderate ( $1,000 \leq \text{Titer} \leq 10,000$ )  
High (Titer > 10,000)

More details will be specified in SAP.

#### **11.4.4.3 Pharmacodynamics**

The values to be used as baselines will be those collected on Day 1 (predose assessments). If any of the scheduled assessments on Day 1 are technically disqualified (eg, insufficient sample), then values determined at Screening can be used as baseline.

For all parameters, raw data, absolute changes from baseline and percent changes from baseline will be summarized in descriptive statistics by treatment group and time point.

Summary plots (mean +/- standard error of the mean) on raw data, absolute changes from baseline and percent changes from baseline will be provided by treatment group.

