### 9.3.2 Pharmacodynamics

Several biomarkers related to asthmatic inflammation and Th2 polarization will be assessed for their value in predicting therapeutic response and/or in documenting the time course of drug response. In a prior asthma trial (ACT11457), treatment with dupilumab significantly suppressed systemic levels of serum TARC (CCL17; a ligand of CCR4 receptors that attracts Th2 cells), plasma eotaxin-3 (CCL26; a ligand of CCR3 receptors that attracts eosinophils and lung mast cells), and serum total IgE (a product of immunoglobulin class switching driven by IL-4), as well as reduced the concentrations of fractional exhaled nitric oxide (a marker of airway inflammation). Now added to these are the following serum biomarkers: eosinophil cationic protein (ECP; a stored protein released from activated eosinophils) and periostin, a protein reported to be elevated at baseline in patients responsive to treatment with anti-IL-13 antibodies.

Assay methodologies are briefly summarized below. More detailed information on the collection, handling, transport and preservation of samples (eg, minimum volumes required for blood collection and for aliquots for each biomarker assay) will be provided in a separate laboratory manual.

Eotaxin-3, eosinophil cationic protein (ECP), total IgE and Thymus and Activation-Regulated Chemokine (TARC) will all be assayed at the same time points as a biomarker set and as indicated in the study flow chart. Periostin and antigen-specific IgE panels will be collected individually per the study flow chart.

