2.4.6.2 Pharmacodynamics/genomics analyses

All biomarkers listed in [Section 2.1.6](#) will be summarized in the Exposed population defined as patients who actually received at least 1 dose or part of a dose of the IMP. Baseline values will be the last value collected prior to the first IMP. For randomized but not treated patients, baseline value will be the last value collected prior to the randomization. Descriptive statistics (including number, mean, SD, median, Q1, Q3, min, max) of biomarkers at baseline will be summarized.

For all parameters including antigen-specific IgEs with a positive (≥ 0.35 IU/mL) incidence of greater than 25% at baseline, values at each visit, absolute change from baseline and percent changes from baseline will be summarized in descriptive statistics by treatment group and time point. Values reported as below the LLQ (lower limit of quantitation) will be imputed as a value one half of the LLQ.

Number and percentage of patients with no positive (≥ 0.35 IU/mL) antigen-specific IgE result, with positive (≥ 0.35 IU/mL) result for only one antigen, and with positive (≥ 0.35 IU/mL) results for at least two antigens will be summarized by treatment group and time point. Same analysis will also be performed using LLQ as the threshold.

Summary plots (mean +/- standard error of the mean) on values at each visit, absolute changes from baseline and percent changes from baseline will be provided for each biomarker by treatment group.

Exploratory analysis of DNA/RNA will be addressed in a separate document.

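### Biomarker plots of mean percent change sit too high in every arm because individual ratios vary; a median or geometric mean ratio should be shown

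*Protocol*

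**What the plan says.** Protocol 11.4.4.3 (Pharmacodynamics) plans two outputs. The first is tabular, per arm and visit: "For all parameters, raw data, absolute changes from baseline and percent changes from baseline will be summarized in descriptive statistics". The second is graphical: "Summary plots (mean +/- standard error of the mean) on raw data, absolute changes from baseline and percent changes from baseline".

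SAP 2.4.6.2 plans the same figures for each biomarker: "Summary plots (mean +/- standard error of the mean) on values at each visit, absolute changes from baseline and percent changes from baseline". It lists median and quartiles for the baseline summary, but asks only for descriptive statistics, without a list, for the by-visit tables. It replaces results below the quantitation limit by half that limit.

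The denominator of the percent change is one measurement. The SAP states "Baseline values will be the last value collected prior to the first IMP". The protocol uses the Day 1 predose value, with the screening value as a fallback if the Day 1 assessment is technically disqualified.

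The markers are positive concentrations or counts. According to Protocol 9.3.2, "Eotaxin-3, eosinophil cationic protein (ECP), total IgE and Thymus and Activation-Regulated Chemokine (TARC) will all be assayed at the same time points"; periostin, antigen-specific IgE, exhaled nitric oxide and blood eosinophils are collected as well. The same section expects suppression: in an earlier asthma trial, "treatment with dupilumab significantly suppressed systemic levels of serum TARC", along with eotaxin-3, total IgE and exhaled nitric oxide.

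For drug levels, Protocol 11.4.4.1 does name a log-scale summary: "Concentrations of functional dupilumab in serum will be summarized using arithmetic and geometric means".

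**The concern.** A percent change cannot fall below -100% but has no upper limit. A chance low baseline followed by an ordinary value gives a large positive figure, while the mirror-image sequence gives a smaller negative one. The two do not cancel in an arithmetic mean, so the mean sits above zero even when nothing has happened.

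Protocol 9.3.2 says the markers are meant partly to document the time course of response. A percent-change curve that rises on placebo while the raw-value curve is flat would mislead readers and leave the report's own figures in disagreement. A reader taking the size of suppression from one arm's percent-change curve would get too small a number. A reader taking the percentage-point difference from placebo would get too large a number.

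**Working it through.** Neither document states a biomarker variance or an expected biomarker change, so there is no planned figure to reproduce. The question is what the planned plot shows when the truth is known.

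**Direction, without a distributional assumption.** Let X0 and X1 be a patient's positive values at baseline and follow-up. If nothing has changed, so that X0 and X1 are exchangeable, then E[X1/X0] = E[(X1/X0 + X0/X1)/2] >= 1, because a positive number plus its reciprocal is at least 2. The expected mean percent change is therefore at or above zero, and strictly above it whenever individual ratios vary.

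**Size, under an assumption.** Take X0 = T·exp(e0) and X1 = T·exp(mu + e1). T is the patient's own level, and e0 and e1 are independent normal errors giving a within-patient CV of c at each visit. Each error has log-scale variance ln(1 + c²), so the log ratio has variance 2·ln(1 + c²), and

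E[percent change] = 100·(exp(mu)·(1 + c²) - 1).

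T cancels. The median change and the geometric-mean change are both 100·(exp(mu) - 1), and this is what "true" means below.

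With mu = 0, c = 0.5 gives 100·(1.25 - 1) = +25%. With mu = ln 0.5, it gives 100·(0.5·1.25 - 1) = -37.5%. The gap column is the difference between the two curves.

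| Within-patient CV (assumed) | Plotted, no change | Plotted, true -50% | Plotted gap (true 50 points) |
|---|---|---|---|
| 10% | +1.0% | -49.5% | 50.5 |
| 20% | +4.0% | -48.0% | 52.0 |
| 30% | +9.0% | -45.5% | 54.5 |
| 50% | +25.0% | -37.5% | 62.5 |

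**Against the plotted error bar.** The SD of percent change with no true change is 100·(1 + c²)·sqrt((1 + c²)² - 1). With all 273 planned patients of one placebo group contributing, the SEM is 0.87, 1.80, 2.86 and 5.67 points for the four CVs. The no-change curve would lie on average 1.2, 2.2, 3.1 and 4.4 SEM above zero.

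**Cause.** Simulations of 2,000,000 patients per setting separate the two candidates.
- Strong between-patient skew (log SD 1.2) and no within-patient variation: mean percent change 0.0%.
- CV 50% with strong skew (log SD 1.2) or with little (log SD 0.2): mean +24.9% in both; median and geometric mean about 0%.
- CV 50% and a true halving: mean -37.5%; median and geometric mean both -50.0%.

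Even symmetric noise produces the effect. With values uniform between 60 and 140 at both visits, E[X1/X0] = 100·ln(140/60)/80 = 1.059, or about +6%.

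**Half-limit substitution.** A patient moving from below the quantitation limit (set to half of it) up to the limit scores +100%; the reverse move scores -50%. Equal numbers moving each way average (100 - 50)/2 = +25% with no net shift.

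**The case against.** The strongest reply is that very little rests on this plot. The biomarker objective is exploratory, no biomarker appears in the SAP's testing hierarchy (Table 6), and the percent-change plot is one of three. The raw-value and absolute-change plots carry no ratio bias and would expose a spurious placebo rise. SAP 2.4.5.3 also gives eosinophils a separate display of mean change by baseline level. All of this stands, and it limits the point to a minor improvement. It does not correct the percent-change plot itself.

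The size is also wholly assumed. At a CV of 10% the bias is about 1 point, and a single CV need not suit every marker. This stands too, which is why the range is shown from the small end.

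It is fair to add that the arithmetic mean correctly estimates the mean percent change. It is simply a different quantity from the typical patient's change, which is what readers will take from the curve.

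Some stronger readings are tempting but not supported:
- **Skewed markers are the cause.** The documents do not say the markers are skewed, and between-patient skew alone gives no bias.
- **The drug effect is understated overall.** This holds only within an arm. Against placebo the percentage-point gap is overstated. With equal CVs the relative contrast is preserved: (1 - 0.375)/(1 + 0.25) = 0.50.
- **SEM bars are wrong in themselves.** They show the precision of a mean, and with 273 to 546 planned per arm symmetric bars are usually reasonable.
- **The plan contradicts its drug-concentration section.** That section summarizes concentrations, not percent change. It shows only that geometric means are already in use.
- **Medians are ruled out.** The by-visit statistics are left unspecified, so medians may well appear in the tables.

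**Conclusion.** The point holds as a low-priority improvement to an exploratory display. The direction is certain for positive markers whose individual ratios vary. The size depends on within-patient variability that the documents do not give, on the lognormal model with equal, independent errors at the two visits, and on taking the median or geometric-mean change as the truth. Under those assumptions the bias is negligible at a CV of 10% and large enough to mislead at 50%. A reader might infer that an efficacy or safety conclusion is at risk; nothing in either document supports that.

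**What to change.** In Protocol 11.4.4.3 and SAP 2.4.6.2, show the percent-change time course either as median percent change with Q1-Q3 or as the geometric mean ratio to baseline (the back-transformed mean log ratio) with 95% CI. The arithmetic mean may stay alongside, and the raw-value and absolute-change plots need no alteration. Name the median in the by-visit biomarker tables.

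State a rule for zero baselines, which can arise for eosinophil counts. The log version needs an offset for zero counts. The median version needs none, but percent change from a zero baseline is still undefined, so those patients must be excluded from that display and their number reported.

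The cost is a few words in two sections and a little plot code. No new data are needed.
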